Date: 1 March 2020

Study Name: Comparison Of The Incidence Of Recurrent Laryngeal Injury Following The Dissection Of The Nerve By Cranio-Caudal And Lateral Approach By Using Introoperative Nerve Monitoring

Study Design: This prospective study was approved by the institutional review board and informed consent was obtained from each patient . A total of 327 patients who were referred to undergo thyroid surgery between June 2018 and November 2019 were assessed for the eligibility to participate in the study. Of these, 233 were considered to be eligible for the study. Exclusion criteria included previous thyroid or parathyroid surgery, substernal goiter, preoperative VCP, evidence of lateral lymph node metastasis, intentional transection of the RLN due to tumor invasion, failure to assess RLN functioning due to equipment issues with the IONM setup, presurgical dissection amplitude of $<500\mu\text{V}$ and patient's refusal to participate in the study. Of 327 patients, 94 were excluded preoperatively due to previous neck surgery (n=47), evidence of lateral neck metastasis(n=24), patient's refusal (n=13) and presence of substernal goiter (n=10). The remaining 233 patients were randomized to have RLN's identified by lateral (n=121) or cranio-caudal approach (n=112 (Figure 1). Computer generated random numbers were generated and printed on cards. These cards were placed in sealed, opaque envelopes. On the morning of operation, one envelope was opened before the operation and, depending of the parity of the number, RLN's of the patient were dissected either by cranio-caudal or lateral dissection during the operation. The patients and the nerves at risk (NAR's) in the lateral and cranio-caudal approach groups were classified as group 1 and 2, respectively. In group 1 and 2, nine and twenty-six patients were further excluded, respectively, owing to intraoperative failure to assess RLN functioning due to equipment issues with the IONM setup or presurgical dissection amplitude of $<500\mu\text{V}$.

Thus, the data of 198 patients were analysed for primary and secondary outcome measures. The primary endpoint was RLN injury and the secondary endpoints included the effect of clinicopathological features, anatomic variations and adverse EMG changes on the occurrence of RLN injury. Of 198 patients, 112 were in the lateral approach group (group 1) and 86 in the cranio-caudal approach group (group 2). Total thyroidectomy or lobectomy was

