performed in 158 (79.8%) and 40 (20.2%) patients, respectively. Sixteen (8%) patients underwent unilateral central lymph node dissection (CLND) additional to total thyroidectomy. Age, gender, body mass index (BMI), the indications for surgery, presence of hyperthyroidism, evidence of autoimmune thyroid disease (ATD) and thyroid lobe volume were recorded in all patients, preoperatively. Thyroid lobe volume was calculated by using the dimensions (length(L), width(W), thickness(T)) of each thyroid lobe measured by ultrasonography according to the following formula; $\pi/6 \times L \times W \times T^{18}$.

All NAR's were dissected by using CIONM including vagal response evaluation at the beginning and at the end of the operation (IONM = L1,V1, R1, R2,V2, L2) according to the recommendations by the International Intraoperative Neural Monitoring Study Group ⁷. All patients underwent pre-, and postoperative laryngoscopic examination within 2 days after surgery, and repeated serially if abnormal (L1, L2). All operations were performed by experienced endocrine surgeons. Length of RLN dissection was defined as extended if the nerve was dissected for 5 cm or greater. Duration of lobectomy for each site, period of time for initial identification of RLN after the mobilization of upper pole on each site, the relationship of the RLN to the ligament of Berry (LOB) and to the Tubercl of Zuckerkandl (TZ) (if present), extralaryngeal branching of the RLN, length of RLN dissection, presurgery and postsurgery amplitude and latency of the vagus and the RLN, occurrence of adverse EMG changes and recovery time or loss of signal (LOS) were recorded intraoperatively in all patients. Serum levels of calcium and parathormone on the first postoperative day were analyzed in all patients. The rates of post-thyroidectomy hypoparathyroidism and vocal cord palsy (VCP) were recorded. Final histopathological diagnosis was documented in all patients, postoperatively.

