Date: 1 March 2020

Study Name: Comparison Of The Incidence Of Recurrent Laryngeal Injury Following The Dissection Of The Nerve By Cranio-Caudal And Lateral Approach By Using Introperative Nerve Monitoring

Statistical Analysis Plan: The Statistical Package for Social Sciences (SPSS) for Windows Version 21.0 (Armonk, NY: IBM Corp.) was used for statistical analysis. The continuous variables are summarised as mean \pm standard deviation. The differences between the groups were assessed using the Student's t-test and a Mann-Whitney U test for normally distributed and non-normally distributed data, respectively. Univariate analysis by Chi-square test was performed to test differences in proportions. Statistically significant results obtained from the univariate analysis were subjected to multivariate logistic regression. A p value <0.05 was considered to be statistically significant.

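### A non-significant primary result on RLN injury would have no planned effect estimate or confidence interval, and with 112 vs 86 patients it could be over-read as equal safety

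*SAP*

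**What the plan says.** The Study Design section of the protocol states: "The primary endpoint was RLN injury". It gives the analysed numbers: "Of 198 patients, 112 were in the lateral approach group (group 1) and 86 in the cranio-caudal approach group (group 2".

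The SAP is a single paragraph, and three of its sentences bear on this comparison:

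- The test: "Univariate analysis by Chi-square test was performed to test differences in proportions".
- The next step: "Statistically significant results obtained from the univariate analysis were subjected to multivariate logistic regression".
- The criterion: "A p value <0.05 was considered to be statistically significant".

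Neither document names a risk difference, risk ratio, odds ratio or confidence interval for any endpoint. Neither gives an expected injury rate, a target difference or a power statement. Neither says how a p-value of 0.05 or more will be interpreted.

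**The concern.** The trial asks whether one dissection route injures the nerve more often than the other. For a harm endpoint, the useful answer is the size of the difference and the largest excess that the data leave open. A p-value gives neither.

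The gap is widest where a reader most needs the interval. If the comparison is significant, the regression step may at least produce an odds ratio. If it is not, the plan stops at the p-value. A trial that has shown the two routes to be close then looks the same as one with too few injuries to tell. Surgeons could take the second for the first and treat the approaches as equally safe.

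**Working it through.** **Flow counts.** There is no sample-size calculation to reproduce, but the patient flow agrees with itself. 327 - 94 = 233 were randomised ("identified by lateral (n=121) or cranio-caudal approach (n=112"). Then "In group 1 and 2, nine and twenty-six patients were further excluded, respectively", so 121 - 9 = 112, 112 - 26 = 86, and 112 + 86 = 198.

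**Inputs.** n = 112 lateral and 86 cranio-caudal (protocol). Alpha = 0.05 (SAP), taken as two-sided because the SAP does not say. Chi-square without continuity correction, because none is mentioned. Injury rates and event counts are my assumptions.

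**Power to detect a doubling, patients as the unit.** Let i and j be the injuries in the two arms and P = (i + j)/198. The test statistic is z = (i/112 - j/86) / sqrt[P(1 - P)(1/112 + 1/86)]. Exact power is the sum of the binomial probabilities of all pairs (i, j) with |z| > 1.96.

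| Assumed rates | Higher risk cranio-caudal | Higher risk lateral |
|---|---|---|
| 3% and 6% | 19% | 15% |
| 5% and 10% | 27% | 23% |
| 10% and 20% | 54% | 49% |

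Fisher's exact test would give less: 15%, 24% and 46% for the middle column. Starting from 5% in the lateral arm, 80% power needs about 17% in the cranio-caudal arm.

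**Nerves as the unit.** The protocol groups both patients and nerves at risk, so the unit is open. Total thyroidectomy or lobectomy was "performed in 158 (79.8%) and 40 (20.2%) patients, respectively". Counting two nerves per total thyroidectomy gives 2 × 158 + 40 = 356. The split by arm is not given. Pro rata it is 356 × 112/198 = 201 and 356 × 86/198 = 155. Ignoring the pairing of nerves within patients, power for the same doublings (higher risk cranio-caudal) is 29%, 44% and 75%. Treating the nerves as independent is optimistic.

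**What an interval would add.** The Newcombe interval for p2 - p1 uses each arm's Wilson limits (l, u):

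- lower = d - sqrt[(p2 - l2)² + (u1 - p1)²]
- upper = d + sqrt[(u2 - p2)² + (p1 - l1)²]

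Take 4/86 cranio-caudal and 5/112 lateral:

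- p2 = 0.0465, Wilson 0.0182 to 0.1136
- p1 = 0.0446, Wilson 0.0192 to 0.1003
- d = 0.0019
- lower = 0.0019 - sqrt(0.0283² + 0.0556²) = -0.061
- upper = 0.0019 + sqrt(0.0671² + 0.0254²) = +0.074
- z = 0.063, p = 0.95

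The same method on two other illustrative results:

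| Cranio-caudal | Lateral | p | 95% interval, percentage points |
|---|---|---|---|
| 6/86 (7.0%) | 4/112 (3.6%) | 0.28 | -3.0 to +11.1 |
| 7/86 (8.1%) | 3/112 (2.7%) | 0.08 | -1.0 to +13.4 |

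The SAP's criterion puts all three results in the same non-significant class. The intervals show that they differ, and that none excludes an excess of 7 percentage points in the cranio-caudal arm.

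**The case against.** A reader might infer that the plan contains a rule equating p of 0.05 or more with no difference. It does not. The SAP defines what counts as significant and is silent on the rest, and neither document makes an equivalence claim. The over-reading is a risk, not something the plan prescribes.

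A reader might also count the absence of a direction or a margin as a defect. An ordinary two-sided comparison for a difference needs neither. A margin would be needed only for an equivalence or non-inferiority claim, and none is made.

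The p-value is not strictly the whole plan, because regression follows a significant result and could give odds ratios. That is fair. But the step does not cover a non-significant comparison, and the SAP does not promise intervals even when it is reached.

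The magnitudes depend on choices that the documents leave open: the injury rate, which arm carries the higher risk, and the unit. It would be wrong to say that a non-significant result is likely whatever the rate. At 10% vs 20% power is 54% with patients and about 75% with nerves. The low figures belong to the 3% to 5% base rates, and nerves raise them without making them adequate.

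Finally, both documents are dated 1 March 2020, recruitment is described as ending in November 2019, and the SAP is written in the past tense. The remedy is therefore a change in analysis reporting, not in design. That limits what it can achieve but does not remove the need for it.

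**Conclusion.** The point stands in this form: no effect estimate or confidence interval is specified for the primary comparison, and a non-significant result would have none at all. The omission is read directly from the SAP and rests on no assumption.

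Its consequence does rest on assumed rates. With patients as the unit and base rates of 3% to 5%, a true doubling would be missed roughly three times in four or more often. At 10% it would be missed about half the time. With nerves as the unit and clustering ignored, it would be missed between about 71% and 25% of the time across the same range. A null p-value in this trial could therefore sit alongside an important excess in either arm, and the plan as written would not show it.

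This should be changed: it is cheap and it decides what a null harm result can be said to mean. An interval would not address the unequal exclusions after randomisation (9/121 = 7.4% vs 26/112 = 23.2%), which are a separate source of bias.

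**What to change.** Amend the SAP, or the analysis report if the analysis is done, as follows:

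- State whether RLN injury is counted per patient or per nerve.
- Make the primary result the risk difference, cranio-caudal minus lateral, with a 95% confidence interval, reported whatever the p-value. Add the risk ratio with its interval. The p-value becomes supporting information.
- If patients are the unit, use a Newcombe or Miettinen-Nurminen interval. If nerves are the unit, use a method that allows for two nerves in one patient, such as GEE or a cluster-robust variance. A plain two-sample interval on nerves would usually be too narrow.
- State that a p-value of 0.05 or more is not evidence of equal injury risk, and that the conclusion will quote both interval limits.
- Date the change and say whether outcome data had been seen.

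Doing the same for loss of signal and hypoparathyroidism is optional. No margin needs to be added unless an equivalence or non-inferiority claim is intended.

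The cost is a few sentences and a line or two of output, with no new data. The one downside is that a null result must be worded more cautiously.

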Demographic data, BMI, the indications for surgery, clinicopathological features, thyroid volume, duration of the operation, period of time for RLN identification, anatomical variations, length of RLN dissection, presurgery and postsurgery amplitude and latency of the vagus and RLN, the rate of adverse EMG changes, LOS and morbidity (vocal cord palsy, hypoparathyroidism) were compared between group 1 and 2. The correlation between intraoperative adverse EMG changes and anatomic variations, lobe volume and type of thyroid disease was investigated as well.

Thyroid surgery and CIONM technique

All operations were performed under general anesthesia by using a small dose (0.3 mg/kg) of non-depolarizing muscle relaxant (Esmeron; MSD Sharp & Dohme GmbH, Haar, Germany) at intubation. The endotracheal tube was properly inserted to ensure that the recording surface electrode was placed at the level of the vocal cords. Prior to lobectomy, the carotid sheath was carefully dissected and the vagus nerve was identified using a hand held stimulation probe. The vagus nerve was dissected over a distance of ≤ 1 cm to place the vagus electrode. (automated periodic stimulation (APS) (Medtronic Xomed, Jacksonville, FL) or saxaphone probe (vagus electrode) ([name] GmbH, Avalanche SI, Germany).

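### One p<0.05 rule covers the primary RLN injury test and about 26 other tests, with no adjustment, testing order or exploratory label

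*SAP*

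**What the plan says.** The Protocol (Study Design) sets out the endpoints: "The primary endpoint was RLN injury and the secondary endpoints included the effect of clinicopathological features, anatomic variations and adverse EMG changes", in each case as they affect the occurrence of RLN injury. The declared secondary endpoints are therefore risk-factor questions, not further comparisons of the two approaches.

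Later in the same section a long list of variables is compared between the arms. It includes "duration of the operation, period of time for RLN identification, anatomical variations, length of RLN dissection, presurgery and postsurgery amplitude and latency" (recorded for both nerves), and ends "the rate of adverse EMG changes, LOS and morbidity (vocal cord palsy, hypoparathyroidism) were compared between group 1 and 2". A further sentence adds: "The correlation between intraoperative adverse EMG changes and anatomic variations, lobe volume and type of thyroid disease was investigated as well".

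The SAP is a single paragraph. It names the t-test, Mann-Whitney U and chi-square tests, sends significant univariate results to multivariate logistic regression, and closes: "A p value <0.05 was considered to be statistically significant". Neither document gives a multiplicity adjustment, an order of testing, or a statement that any analysis is exploratory or descriptive.

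**The concern.** Naming a primary endpoint protects a trial's conclusion only if the analysis plan treats that endpoint differently from the rest. Here it does not. Followed as written, p = 0.04 for identification time, loss of signal or hypoparathyroidism earns the same description as p = 0.04 for RLN injury.

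Two kinds of claim are exposed. If RLN injury does not differ between approaches, the plan still permits one approach to be called significantly better on some other outcome. And any one clinical or anatomic variable could be called a significant risk factor for RLN injury. Readers would attach a 5% error rate to either claim, although each is the pick of a family of tests.

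**Working it through.** The plan states no overall error rate, so there is no figure of its own to reproduce. The check is a count of tests followed by a family-wise error calculation.

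**Counts, from the Protocol's Study Design section**

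- *(a) Between-arm outcomes other than RLN injury.* Operation time, time to identify the nerve and dissection length (3); amplitude and latency after surgery, each for vagus and RLN (4); adverse EMG rate, loss of signal and hypoparathyroidism (3). Total 3 + 4 + 3 = 10. Vocal cord palsy is taken to be the primary outcome; counted separately, it makes 11.
- *(b) Candidate risk factors for RLN injury.* Seven clinical variables ("Age, gender, body mass index (BMI), the indications for surgery, presence of hyperthyroidism, evidence of autoimmune thyroid disease (ATD) and thyroid lobe volume") and three anatomic ones ("the relationship of the RLN to the ligament of Berry (LOB) and to the Tubercl of Zuckerkandl (TZ) (if present), extralaryngeal branching" being the third) give 7 + 3 = 10. Adding either final histology or adverse EMG changes gives 11; adding both gives 12.
- *(c) EMG correlations.* Three anatomic variations, lobe volume and disease type: 3 + 1 + 1 = 5.

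Together these are 10 + 11 + 5 = 26 tests besides the primary. Baseline comparisons and presurgery EMG values are left out, so the counts lean low.

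**Formulas**

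With m independent tests at 0.05 and every null true, the chance of at least one p<0.05 is 1 − 0.95^m:

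- m = 5: 1 − 0.774 = 0.226
- m = 10: 1 − 0.599 = 0.401
- m = 11: 1 − 0.569 = 0.431
- m = 12: 1 − 0.540 = 0.460

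For correlated tests, take two-sided z statistics with a common correlation ρ. Given a shared standard normal factor u, the tests are independent, so the chance is

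1 − ∫ φ(u) [Φ((1.96 − √ρ·u)/√(1−ρ)) − Φ((−1.96 − √ρ·u)/√(1−ρ))]^m du.

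**Results**

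| Family | m | ρ = 0 | ρ = 0.5 | ρ = 0.8 |
|---|---|---|---|---|
| (a) Between-arm outcomes | 10 | 40.1% | 28.7% | 17.3% |
| (b) Risk factors for injury | 11 | 43.1% | 30.4% | 18.0% |
| (c) EMG correlations | 5 | 22.6% | 18.3% | 12.7% |

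The documents give no correlations, so ρ is an assumption throughout. Sidedness is not stated either; two-sided was assumed.

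**Two qualifications on family (b)**

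- The figure describes the univariate screen. The logistic regression that follows may drop some confounded factors, but it is fed by the screen and does not control the screen's false positives.
- If injuries are very rare, the chi-square test can fall below its nominal level. As an illustration with the analysed split of 112 and 86 patients, exact enumeration gives an actual size of 2.1% at an assumed injury rate of 1%, and 4.6% to 5.5% at assumed rates of 2% to 10%. Rarity would lower the injury-based figures; it would not affect families (a) and (c), whose outcomes are not RLN injury.

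**The case against.** The strongest reply is that a primary endpoint is named, its single test at 0.05 needs no correction, and leaving other outcomes unadjusted beside one primary is common practice. That stands for the primary result. A reader might infer from the number of tests that the RLN injury comparison is itself unreliable; the documents do not support that. The common practice, though, depends on the other results being presented as supportive, and nothing in the plan says so.

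Second, the between-arm list mixes outcomes with demographics and reads partly as a descriptive table. No text says that any of these would be used to declare an approach superior. That is fair: the plan permits such a claim, but does not state an intention to make it.

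Third, the EMG correlations are described in an exploratory tone and the SAP names no correlation method. Counting five tests at full alpha is therefore a reading, and family (c) is the weakest of the three.

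Fourth, a reader might conclude that a chance finding somewhere is more likely than not. Pooling the primary with families (a) and (b) makes 22 tests, and 1 − 0.95^22 = 67.6% under independence. At ρ = 0.5 in one block it falls to 44%. Whether the figure passes one half thus rests on a correlation the documents do not give. Nor does the SAP promise a 5% family-wise rate that is then broken; it sets only a per-test threshold.

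**Conclusion.** The concern holds for everything outside the primary comparison. The plan identifies its primary endpoint but gives that status no effect in the analysis, so secondary and unclassified comparisons carry the same claim as the primary.

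If all nulls are true, the chance of at least one false claim is about 17–40% for the 10 between-arm outcomes, 18–43% for the 11 risk factors and 13–23% for the 5 EMG correlations. These rest on the counts above, two-sided tests and an assumed common correlation between 0.8 and 0. A 12th risk factor would raise the upper end of that family to 46%. Every family stays well above 5% across the range, subject to the caution about very rare injuries in family (b).

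This should be corrected, but it leaves the error rate of the primary test untouched.

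**What to change.** Replace the last sentence of the SAP with:

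> *The only confirmatory test is RLN injury, lateral versus cranio-caudal, at two-sided 0.05. All other between-arm comparisons are reported as differences with 95% confidence intervals, labelled exploratory, and not used to conclude that either approach is superior. Risk-factor analyses and EMG correlations are hypothesis-generating and labelled so.*

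Carry the same labels into the table footnotes. One confirmatory test at 0.05 then leaves a 5% false-positive risk for the confirmatory claim.

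A gatekept Holm procedure for the other outcomes is not recommended. Both documents are dated 1 March 2020, after the June 2018 to November 2019 referral period, and describe enrolment and analysis in the past tense. A testing order added now would not be prespecified, so it could not supply the error control it appears to offer. Labelling remains sound.

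The cost is wording only, with no new data. The sponsor gives up the right to present a secondary outcome or risk factor with p<0.05 as an established finding.
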